2.2 STUDY DESIGN

Participants will be recruited from the ambulatory IPF patient populations among the collaborating institutions.

Following completion of screening and eligibility assessments, N=58 subjects will be randomly assigned to one of two cohorts intended to receive either rituximab or placebo, in a ratio of 1:1. The rituximab (or placebo) will be administered over two doses (1 g each), following premedications, with a 14 day interval in between these replicate treatments.

All patients will have physiological assessments that are standard of care for IPF patients, including initial chest radiographs (CT scans) and serial pulmonary function tests (spirometry, diffusion capacity, 6 minute walk distance). These procedures and routine laboratory tests will not be repeated specifically for this study if they are deemed to be clinically indicated. The results of these standard of care procedures will be extracted from the participant's medical record and used as research data. All enrolled subjects will also have serial measures of circulating autoantibodies.

Patients will be monitored carefully for occurrences of adverse events. Adverse experiences will be evaluated according to criteria outlined in the NCI Common Terminology Criteria for Adverse Events (CTCAE), version 4.0.

Patients will be followed for nine (9) months after random assignment. Patients removed from treatment due to unacceptable adverse events will be followed throughout the 9 months under the principle of intent to treat.

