2.4 RANDOMIZATION

Following a determination of eligibility, subjects will be randomly assigned to one of two treatment arms (1:1 ratio), after stratification on the basis of gender, disease severity (DLCO <35% of predicted values), and current use of either/both pirfenidone and/or nintedanib. These stratifications will ensure ~equal proportions of severely ill patients, and ~equal proportions of males, in each arm. Male IPF patients have worse prognoses than females (1-4). Randomization assignments will be made in random block sizes of 2 and 4.

Randomizations will occur on the day of initial treatment, to reduce the possibility of "wasting" a randomization on a patient who fails to return for treatment.

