2.8.2. Secondary End-Points

Secondary end-points are: a.) treatment-related effects on anti-HSP70 concentrations, b.) forced vital capacities, c.) incidences of acute IPF exacerbations, d.) survival durations, e.) hospitalization rates, and f.) adverse event-rates.

- a.) Anti-HSP70 IgG concentrations- We have found anti-HSP70 is ONE OF MANY autoantibodies present in IPF patients, and it happens too to be ONE OF SEVERAL associated with IPF progression (14). Thus, we will be able to test for effects of rituximab on both global autoantibody production (Primary Endpoint), as well as its effects on a particular, clinically-associated specific autoantibody (anti-HSP70), pretreatment and 1,3,6 and 9 months post-treatment. Anti-HSP70 IgG will be measured by ELISA, as detailed in citation #14.
- **b.)** Forced vital capacities (FVC) by spirometry- In addition to FVC, other pulmonary function variables that are not formal endpoints (FEV $_1$, DL $_{CO}$, and O $_2$ requirement at rest and with walking), 6 minute walk distance, and Borg Dyspnea Assessments will be routinely measured pretreatment and at 1,3,6, and 9 months thereafter. These tests are standard operating procedures (SOP) for care of IPF patients at our centers.
- **c.)** Acute exacerbation frequencies- IPF patients typically experience slowly progressive, if somewhat episodic, lung function deterioration. Nonetheless, a sizeable proportion, variously estimated as 10-to-50% or more, develop acute exacerbations that can result in very rapid onset respiratory failure and death within days (4). Results of studies indicate that autoantibodies are involved in acute exacerbations of IPF. It is hoped that rituximab therapy will decrease the frequency or delay onset of acute exacerbations. Acute exacerbations will be defined by

participating physicians using current consensus criteria, i.e., worsening hypoxemia and dyspnea within the preceding 30 days, characteristic new radiographic pulmonary infiltrates, and no other evident cause of lung dysfunction after thorough clinical assessments (4).

- **d.)** Survival- Given the high mortality of IPF patients, efficacy of the experimental therapy could result in prolonged survival among treated subjects. Survival durations from study enrollment will be tabulated as both absolute survival and transplant-free survival.

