- **e.) Hospitalizations** Indirect evidence of treatment efficacy could also be discerned by reductions of subsequent needs for hospital admissions. The frequencies and durations of hospitalizations among trial subjects will be tabulated and analyzed.
- **f.) AE Monitoring-** The National Cancer Institute Common Toxicity Criteria Scale will be used to define grades (severity) of AE and toxicities. An AE is defined as any untoward medical occurrence in a subject, regardless of its relationship to these treatments. Toxicity is an AE with a direct relationship to the study drug. All toxicities are AE, but not all AE are toxicities.

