2.9 DATA AND POWER ANALYSES

2.9.1 Power Analyses:

Given the initial nature of this trial, definitive power calculations are speculative. Nonetheless, even moderate efficacy of the experimental treatment (as we anticipate) will produce evidence of same. Assuming a type 1 error rate of 0.05, a two-sided alternative hypothesis, n = 29/arm, and very conservative event rates (i.e., reduction of autoantibody titers in 33% of the experimental arm subjects, and 3% reduction in placebo controls) there is 80% power to detect a statistically significant effect.

The sample size of 58 for this clinical trial is based on exposing a minimum number of patients to potential risks of the experimental treatment, while still obtaining useful information. Analyses will follow intention to treat principles. Missing data techniques (e.g., multiple imputation) will be employed for subjects lost to follow-up, had transplants, or those who died. A sensitivity analysis will also be conducted in which transplantations and deaths will be considered failures.

2.9.2 Data Analyses:

Data analyses begin by describing baseline demographic and medical characteristics of the cohorts. Descriptive statistics, including measures of central tendency and dispersion, will be computed for continuous data (e.g., age). Frequency distributions will be estimated for categorical data (e.g., gender). To ensure balanced random assignments, treatments are examined in relationship to demographic and medical characteristics using the appropriate parametric (e.g., t-test) or nonparametric test (e.g., chi-square, Wilcoxon tests). Reduction of autoantibody titers from baseline to the nine-month follow-up visit will be calculated as a binary indicator (yes/no). A Fisher's Exact test will be used to compare rates of autoantibody titer reductions between the two groups. To control for the stratification variables, an exact logistic regression model will be used, including main effect for treatment and the stratification variables. Unbalanced baseline characteristics will also be included in the regression model.

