Linear regression models will be used to assess the treatment effect on continuous variable secondary endpoints. Main effects will include treatment, the stratification variables, and unbalanced baseline characteristics. Both the proportion of individuals with AEs and the count of AEs per person will be compared by treatment. A logistic regression model will be used to compare the proportion of subjects with acute exacerbations, hospitalizations, or adverse events (AEs) by treatment group, with main effects as described above. A negative binomial model will be used to evaluate the average count of AEs per subject by treatment group. For all models, the model assumptions (e.g., normality of residuals, over dispersion) will be investigated. If the assumptions are violated, transformations will be investigated. If adequate transformations cannot be identified, nonparametric approaches will be utilized. Small cell sizes may exist and exact methods may need to be employed.

Additional exploratory analyses will be conducted. This may include the use of mixed-effects regression models to examine the longitudinal course of the outcomes as well as survival analyses (e.g., Kaplan-Meier curves, log-rank test, Cox proportional hazards models) to evaluate time to event outcomes, such as time to death.

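### Hospitalizations and acute exacerbations have only a yes/no logistic model firmly specified; a count model for admissions and a time-to-first-exacerbation analysis should be named

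*Combined protocol and SAP*

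**What the plan says.** Section 2.8.2 lists the incidence of acute exacerbations and hospitalization rates among the secondary endpoints. On exacerbations it adds: "It is hoped that rituximab therapy will decrease the frequency or delay onset of acute exacerbations". On admissions it says: "The frequencies and durations of hospitalizations among trial subjects will be tabulated and analyzed".

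Section 2.9.2 then assigns the models. For both endpoints: "A logistic regression model will be used to compare the proportion of subjects with acute exacerbations, hospitalizations", with treatment, the stratification factors and unbalanced baseline characteristics as main effects. Adverse events get the same logistic model and also a negative binomial model for the count per subject. A general sentence gives linear regression to continuous secondary endpoints. It could be read to cover length of stay, but it does not name it. Kaplan-Meier, log-rank and Cox methods appear as possible exploratory work, with time to death as the one example.

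Follow-up is common to all subjects: "Patients will be followed for nine (9) months after random assignment" (Section 2.2). Section 2.9.1 plans missing-data techniques, with multiple imputation as an example, for subjects who are lost, transplanted or dead. It adds a sensitivity analysis that scores transplant and death as failures. It does not say which endpoints these rules cover.

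**The concern.** A rate and a delay are described, but a proportion is modelled. A subject admitted five times contributes the same as a subject admitted once, and an exacerbation in month 1 the same as one in month 9. The plan recognises this difference for adverse events, where it compares both the proportion and the count, but does not do so for admissions.

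Two things are at stake. First, information is discarded in a trial of 58 subjects. Second, the handling of death and transplant for these two endpoints is open. An analyst could leave early deaths as having no event, impute admissions or exacerbations after death, or score deaths as failures, and each could be defended from Section 2.9.1. The trial is meant to inform a Phase III design, and Section 1.2 names fewer exacerbations as a hoped-for benefit, so these estimates will be used even though they are secondary.

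**Working it through.** **The plan's own figure.** Section 2.9.1 states "Assuming a type 1 error rate of 0.05, a two-sided alternative hypothesis, n = 29/arm", with "reduction of autoantibody titers in 33% of the experimental arm subjects, and 3% reduction in placebo controls", and concludes "there is 80% power to detect a statistically significant effect". Full enumeration of the two-sided Fisher exact test gives 81.0%, so the figure reproduces. It concerns the primary endpoint only; no power is stated for admissions or exacerbations.

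**Inputs for the check.**
- 29 per arm, 9 months, two-sided 0.05 (Sections 2.9.1 and 2.2).
- Death: Section 1.3 gives a median survival of about 3 years from diagnosis. With a constant hazard, μ = ln 2 / 36 = 0.01925 per month and 9-month mortality is 1 − exp(−9μ) = 15.9%, about 4.6 of 29 per arm.
- Exacerbation: Section 2.8.2 cites 10% to 50% or more, with no time window. 10%, 30% and 50% are used here as assumed 9-month risks without death, λ = −ln(1 − risk)/9.
- Admissions: no rate is given. Means of 0.4 and 0.8 per control subject over 9 months, with gamma dispersion 1 or 0.5, are assumptions. A halving by treatment is assumed for both endpoints.

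**First exacerbation: time versus yes/no.** P(event seen) = λ/(λ+μ) × [1 − exp(−9(λ+μ))]. At 30% risk, λ = 0.03963 and P = 0.277 in control. With λ halved, P = 0.150. Expected events D = 29 × (0.277 + 0.150) = 12.4. Schoenfeld power = Φ(0.693 × √12.4 / 2 − 1.96) = Φ(−0.74) = 23%. The normal test of 0.277 v 0.150 has 21%.

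| Assumed risk | Time to first event | Yes/no |
|---|---|---|
| 10% | 10% | 10% |
| 30% | 23% | 21% |
| 50% | 36% | 33% |

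The gain is 0 to 3 points.

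**Admissions: rate versus yes/no.** Trials were simulated with a rate ratio of 0.5 and follow-up cut by death at hazard μ in both arms. The rate ratio used person-time and a robust standard error, as a stand-in for the negative binomial model. The yes/no test was unadjusted.

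| Control mean, dispersion | Rate | Yes/no |
|---|---|---|
| 0.4, 1 | 21% | 17% |
| 0.8, 1 | 34% | 20% |
| 0.8, 0.5 | 40% | 26% |

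The gain is about 4 to 14 points. One caution: the same simulation rerun with a rate ratio of 1 (10,000 trials per setting) rejected in 5.9% to 6.7% of trials for the rate test and 4.4% to 4.9% for the yes/no test. Part of the gap is therefore size, not efficiency.

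**Effect of deaths on the odds ratio, if deaths are left as no event.** With equal mortality and no treatment effect, the odds ratio is exactly 1.00. If treatment halves the death hazard, then at 30% risk P = 0.288 v 0.277 and OR = (0.288/0.712)/(0.277/0.723) = 1.06. Over 10% to 50% risk the range is 1.05 to 1.07; with the hazard cut to a quarter it is 1.07 to 1.11. For scale, at 30% risk the standard error of the log odds ratio is √{2 × [1/(29 × 0.277) + 1/(29 × 0.723)]} = 0.59, so a null result carries a 95% interval of roughly 0.32 to 3.2.

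**The case against.** The strongest reply is that the plan is less bare than it looks. The listed exacerbation endpoint is incidence, and the proportion with an event over a fixed 9 months is an ordinary measure of it; the words on delay express a hope, not a definition. Survival methods are allowed and time to death is only an example. Section 2.8.2 does promise an analysis of admission frequency and duration. Section 2.10.2 calls clinical effects speculative in a trial of this size. Most of this stands, and it is why the point is small for exacerbations. It does not supply a count or rate model for admissions, and an optional analysis that names neither endpoint is not a prespecified one.

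A reader might go further and infer that the logistic odds ratio is biased because early deaths count as event-free over unequal follow-up. The documents do not support that. Planned follow-up is the same for all, including subjects taken off treatment for adverse events, and is shortened only by death, transplant or loss. No section scores early exits as event-free; Section 2.9.1 plans missing-data methods and a failure-based sensitivity analysis. Extreme exit rates such as 5% v 30%, which would give odds ratios of 1.17 to 1.27 under no effect, appear nowhere in the plan. Nor would cumulative incidence curves remove such a gap: the formula for P above is the cumulative incidence with death as a competing event, so the curves would show the same difference. Only the cause-specific hazard separates the two.

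**Conclusion.** The point holds in a limited form. The only model firmly specified for admissions and exacerbations ignores repeats and timing, while a suitable count model already sits in the same section for adverse events. The loss is mainly for hospitalizations, about 4 to 14 power points. For first exacerbation it is 0 to 3 points, and the case there is that the analysis should match the stated aim. Distortion of the odds ratio by deaths needs two conditions, deaths left as no event and exit that differs by arm. Even then it is small beside the imprecision at 29 per arm.

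These sizes rest on constant hazards, independence of exacerbation and death within arm, mortality derived from survival since diagnosis, and event rates that the documents do not give. Power is low under every method (10% to 40%), so none of this makes the secondary endpoints confirmatory. The primary endpoint and its conclusion are unaffected.

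**What to change.** In Section 2.9.2:
- Analyse the number of hospitalizations per subject with the negative binomial model already planned for adverse events, with log follow-up time as offset. State how length of stay will be summarised.
- Prespecify time from randomization to first acute exacerbation in a cause-specific Cox model, with death and transplant ending follow-up for the event. Show cumulative incidence curves descriptively.
- State that events are not imputed after death for these two endpoints, and say which endpoints the missing-data and failure rules of Section 2.9.1 cover.
- Keep the logistic models as supportive.

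The cost is a few sentences and a little programming. Admission and exacerbation dates must be recorded on the case report form: the monthly contacts in Section 2.6 collect interval histories, but these dates are not listed. The downside is wide intervals, and possibly an unstable dispersion estimate, if events are few.

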Research records for each case should contain copies of the source documents for the data reported to DCC. If data are abstracted from medical charts that are not filed at the investigative sites (e.g. hospital charts), copies of these records should be filed in the research chart. All source data stored in the research charts must be identified only by the Study ID. Any names, contact information, medical record numbers, or other identifying information must be masked prior to copying. Every attempt must be made to obtain all records/charts that were used to abstract any study data for this protocol at the time of the audit visit. This will prevent any discrepancies and provide the ability to verify the document and the data reported.

Every effort will be made to collect complete data for each study visit. Causes of *missing data* will be fully documented. With respect to safety evaluation, it is not planned to impute missing data.

Research charts must be kept in a location separate from the clinical records used to contact patients and schedule appointments. No personal identifying information shall be kept within the research charts.

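### The adverse-event count model in 2.9.2 takes no account of time observed, so its ratio is biased if follow-up is shorter in one arm.

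*Combined protocol and SAP*

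**What the plan says.** Section 2.8.2 lists AE rates among the secondary endpoints ("d.) survival durations, e.) hospitalization rates, and f.) adverse event-rates"). Section 2.9.2 turns this into two comparisons: "Both the proportion of individuals with AEs and the count of AEs per person will be compared by treatment". The count is to be modelled as follows: "A negative binomial model will be used to evaluate the average count of AEs per subject by treatment group". The model terms given in that section are these: "Main effects will include treatment, the stratification variables, and unbalanced baseline characteristics". No offset, exposure or person-time term for AEs appears there or elsewhere in the protocol.

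On follow-up, Section 2.2 says "Patients will be followed for nine (9) months after random assignment", and adds "Patients removed from treatment due to unacceptable adverse events will be followed throughout the 9 months under the principle of intent to treat". Section 2.9.1 foresees incomplete follow-up: "Missing data techniques (e.g., multiple imputation) will be employed for subjects lost to follow-up, had transplants, or those who died". Section 6.7.2 takes safety out of that provision: "With respect to safety evaluation, it is not planned to impute missing data".

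**The concern.** A count per subject measures a rate only when subjects are observed for equal time. Here the plan itself expects some to be observed for less than nine months. Imputation is ruled out for safety, so an unobserved month adds no events and is treated like a month in which nothing happened. Survival is also listed as a secondary endpoint that treatment might change, so the plan allows that treatment could alter the observation time behind the AE comparison.

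The error can go either way. If the rituximab arm has more early exits, a true excess of AEs is understated. If the placebo arm has more, an excess is created or enlarged. The other analyses do not correct this. The logistic model for the proportion with any AE ignores time as well. The time-to-event methods are exploratory, with time to death as the example. The listed assumption checks, normality and over-dispersion, would not show an imbalance in exposure.

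**Working it through.** The documents give no figure for the AE model, so there is none to reproduce. The one stated power, 80% for the primary endpoint, reproduces (81.0% by exact enumeration of Fisher's test at 33% v 3%, 29 per arm), but it has no bearing here.

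**Inputs.** From the protocol: planned follow-up T = 9 months; 29 per arm; median survival about 3 years from diagnosis (1.3); infusions on Day 1 and Day 14 (2.6.2). Assumed, because the documents are silent: the fraction f of an arm gone by nine months, AE rates, and dispersion.

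**Step 1: is early exit plausible?** With exponential survival and a 36-month median, the proportion dead by nine months is 1 - 2^(-9/36) = 16%. This is only illustrative, since subjects may enter up to five years after diagnosis.

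**Step 2: mean follow-up.** For exponential exit, mean follow-up = f × T / (-ln(1 - f)).

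- f = 10%: 0.9 / 0.1054 = 8.54 months
- f = 16%: 8.26 months
- f = 20%: 1.8 / 0.2231 = 8.07 months
- f = 30%: 2.7 / 0.3567 = 7.57 months
- f = 40%: 3.6 / 0.5108 = 7.05 months

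**Step 3: expected ratio without an offset.** With a constant AE rate, this is the true ratio times the ratio of mean follow-up. For a true ratio of 1.00:

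| Exit, placebo v rituximab | Ratio of mean follow-up | Expected AE ratio |
|---|---|---|
| 10% v 10% | 8.54/8.54 | 1.00 |
| 10% v 20% | 8.07/8.54 | 0.94 |
| 16% v 30% | 7.57/8.26 | 0.92 |
| 10% v 30% | 7.57/8.54 | 0.89 |
| 10% v 40% | 7.05/8.54 | 0.83 |

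With a true ratio of 1.25 and 10% v 30% exit, the expected ratio is 1.25 × 0.886 = 1.11.

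**Step 4: simulation** (1,000 trials per setting, dispersion estimated). Assuming 4 AEs per nine months, dispersion 1 and 10% v 30% exit:

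- True ratio 1.00: the estimate is 0.88 without an offset and 0.99 with one. False-positive rates are 8.1% and 7.7%.
- True ratio 1.25: the estimate is 1.10 without and 1.24 with. The difference is detected in 6.1% and 13.1% of trials.
- Exits reversed, true ratio 1.00: the estimate is 1.13 without and 1.01 with.

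A harsher setting has 20% of one arm leaving at month 1 and none of the other (0.6 AEs per month, dispersion 0.3). Without the offset the ratio is about 0.81 and the false-positive rate about 15%; with it, about 0.99 and 6%. At 16% v 30% exit there is almost no inflation of the false-positive rate.

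**Step 5: does a single offset suffice?** Take the same month-1 exits and let s be the share of nine-month AEs that falls in month 1. With no true difference:

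- Count ratio = 0.8 + 0.2s, which is 0.88 at s = 40% and 0.92 at s = 60%.
- Person-time ratio = (0.8 × 9 + 0.2 × 1) / 9 = 0.82.
- Pooled rate ratio = 0.88/0.82 = 1.07 and 0.92/0.82 = 1.12.

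A negative binomial fit gives subjects with short follow-up more weight than pooling does. In simulation a single offset moved the null ratio to about 1.19-1.35. Splitting at month 1 removes this: every subject has a full first month, so that ratio is 1, and only subjects still observed contribute later, so that ratio is also 1.

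**The case against.** The case for leaving the plan alone has five parts.

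- **Differential exit is partly designed out.** Subjects who stop treatment because of AEs stay in follow-up, people unwilling to complete nine months of surveillance are excluded, and telephone calls cover the months without visits. This stands. It leaves death, withdrawal, loss and possibly transplant as routes.
- **The size is modest.** This also stands. At 10% v 20% exit the bias is about 6% and the false-positive rate hardly moves. A reader might infer that the plan produces many false safety signals. Only extreme, assumed exit patterns do that, and nothing in the documents supports them.
- **Count per subject over a fixed nine months is a legitimate intention-to-treat summary.** That is a reason to keep it, but it does not make it a rate, which is what 2.8.2 names.
- **The plan is silent on an offset and does not exclude one.** True, but silence leaves the choice open until after the data are seen.
- **An offset carries its own risk.** This is the strongest point. A reader might infer that adding log(time) costs nothing. With two infusions in the first two weeks, and with infusion reactions among the common risks in 5.1.2, the AE rate may be far from constant. A single offset can then push the ratio the other way, as Step 5 shows. This changes the remedy but leaves the gap in place.

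**Conclusion.** The gap is real and nothing else in the protocol closes it. It should be fixed, but it is a moderate problem in a secondary endpoint and does not touch the primary conclusion. The bias equals the ratio of mean follow-up when AE rates are constant: about 6% for 10% v 20% exit, 11% for 10% v 30% and 17% for 10% v 40%. With equal exit it is nil. If AEs cluster early, the bias in the count is smaller.

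A reader might go further and conclude that the AE comparison in this trial will be biased, or that rituximab will look safer than it is. The documents do not support either. They give no exit rates by arm, and the direction depends on which arm has the shorter follow-up. The exit fractions, AE rates, dispersion and share of early AEs used here are all assumptions. The absence of any follow-up-time term and the direction of the bias, given unequal follow-up, do not depend on them.

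**What to change.** In 2.9.2:

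1. Fit the negative binomial model with a log(follow-up time) offset. Time runs from first treatment to the last AE contact, death, withdrawal or Month 9, whichever comes first. State how transplant is handled.
2. Count AEs and person-time separately for the first month and for months 1-9, using a period term with each period's own offset. Define the cut as a fixed day from first treatment, and allow for correlation between a subject's two records.
3. Report AEs per person-month by arm and period.
4. Keep the planned count per subject alongside.

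No new data are needed. Appendix A has an AE assessment at every visit and call, and 2.9.3 provides for logging early exits. The cost is a short paragraph in the plan and slightly more analysis. Two assumptions remain and should be stated: a constant AE rate within each period, and exit that is uninformative about AEs, which is least secure for deaths.
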